1 STUDY SYNOPSIS

<copy this information from last approved protocol>

Complete Protocol Title	Quattro® X Suture Anchor with BroadBand™ Tape Post Market Clinical Follow-up Study (incl. Instruments)
Protocol Number	CME2021-24SM
Short Protocol Title	Quattro® X with BroadBand
Sponsor	Zimmer Biomet, Warsaw, Indiana, United States
Manufacturer	Cayenne Medical Inc.
Study Device(s)	Quattro X Suture Anchors with BroadBand Tape - 5.5mm Quattro X Suture Anchor Double-Loaded with BroadBand Tape (Non-Sliding)
	- 6.5mm Quattro X Suture Anchor Double-Loaded with BroadBand Tape (Non-Sliding)
	- 5.5mm Quattro X Suture Anchor Double-Loaded with BroadBand Tape (Sliding)
	- 6.5mm Quattro X Suture Anchor Double-Loaded with BroadBand Tape (Sliding)
	Quattro X Suture Anchor Reusable Instruments (Non-Sterile)
	- Awl, 5.5/6.5mm Quattro X Suture Anchor
	- Tap, 5.5mm Quattro X Suture Anchor
	- Tap, 6.5mm Quattro X Suture Anchor
	The objective of the study is to collect data confirming safety, performance and clinical benefits of the Quattro® X Suture Anchor with BroadBand™ Tape and Instruments when used in rotator cuff repair.
Study Objectives/Endpoints	The primary endpoint of this study is the assessment of performance by analyzing soft tissue to bone healing in the shoulder (rotator cuff). Healing will be assessed by the investigator using PROMs and clinical outcomes of the patient.
	The clinical benefit will be assessed by functional outcomes measured using standard and well-established scoring systems (e.g. Constant & Murley and EQ-5D-5L) at 1 year post-operative.
	The safety will be assessed by monitoring the incidence and frequency of device- and/or procedure-related adverse events.

Indications/Target Population	Subjects treated with the Quattro® X Suture Anchor with BroadBand™ Tape for rotator cuff repair, according to the IFU and who meet all of the inclusion and none of exclusion criteria.

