2 STATISTICAL ANALYSIS PLAN

2.1 Sample Size

The overall success rate will be calculated based on the percentage of subjects who have successful healing. The following hypothesis will be tested by the exact binomial test

H0: $E1 - E0 \le - \delta E$

Ha: E1 – E0 > - δ E

Where:

E0 = 85%, the expected success rate of similar devices

E1 = the success rate in the Quattro® X Suture Anchor with BroadBand™ Tape treatment group

 $\delta E = 0.10$, non-inferiority margin for healing

In addition, one-sided 95% exact confidence Interval (CI), lower limit of the success rate, will be calculated.

Based on the hypothesis test above, 103 subjects will provide approximately 80% power for the one-sided exact binomial test at 0.05 significant level. The sample size was calculated using SAS for Windows version 9.4. To account for an expected 5% loss-to-follow up, 109 patients will be enrolled.

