2.3 Data Analysis

The Per Protocol population will be defined as those subjects that undergo a successful implantation of the Quattro® X Suture Anchor with BroadBand™ Tape. Analyses on the primary and secondary endpoints will use this population as well as any exploratory analyses.

The primary endpoint will be determined at the only clinical assessment, about one year from the index surgery. The absence of a revision surgery or re-tear not previously noted on the case report form will denote a success (within 425 days from index surgery). All other cases will be a failure and have a documented revision surgery or re-tear.

Secondary analyses will include a summary of any clinical scores captured at baseline and the one year assessment; change from baseline analyses may be developed. In addition, a summary of medications and patient satisfaction may also be assessed.

Any potential exploratory analysis that assess outcomes be categories (gender, age, etc.) will use appropriate statistical test for the type of variable (i.e. t-tests, ANOVA, Fisher's Exact, etc). All testing will use a Type I error of 0.05 and no p-values will be adjusted for multiplicity.

Adverse events will also be captured at the one year assessment. Only AEs that occur on or after the index surgery and before any potential revisions or re-tears will be summarized. Adverse events will be presented as the number of cases for each AE and the number of times the give AE occurred. Finally, a complete listing of all AEs will be presented.

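### The adverse event table stops at the first revision or re-tear, so it cannot report the incidence that the safety objective names

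*Combined protocol and SAP*

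**What the plan says.** The synopsis (Section 1, Study Objectives/Endpoints) states the safety objective: "The safety will be assessed by monitoring the incidence and frequency of device- and/or procedure-related adverse events". It sets no end point at failure of the repair.

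Section 2.3 (Data Analysis) then defines what is counted: "Only AEs that occur on or after the index surgery and before any potential revisions or re-tears will be summarized". The format of the counts follows: "Adverse events will be presented as the number of cases for each AE and the number of times the give AE occurred". The section closes with an output that has no stated cut-off: "Finally, a complete listing of all AEs will be presented".

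Two other statements in Section 2.3 bear on the point. On timing of capture: "Adverse events will also be captured at the one year assessment". On what counts as failure: "All other cases will be a failure and have a documented revision surgery or re-tear". No reason is given for the cut-off, and no table is planned for AEs at or after a failure.

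**The concern.** The rule that ends AE counting is triggered by the study outcome. A subject whose repair holds contributes every AE up to the one-year assessment. A subject whose repair fails contributes only those dated before the failure. The table is therefore incomplete only among failed repairs, where device- or procedure-related harm is of most interest, and the error runs in one direction: counts can fall but never rise.

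The failure event may be lost as well. A revision or re-tear does not occur before itself, so if it is recorded as an AE, the wording excludes it.

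At stake is whether the safety table reports the quantity that the synopsis promises. A reader wanting the untruncated incidence would have to rebuild it by hand from the listing.

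**Working it through.** **Comparison of the two statements**

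| Item | Synopsis, safety objective | Section 2.3, AE summary |
|---|---|---|
| Quantity | incidence and frequency | subjects with each AE, and occurrences |
| Start | not stated | index surgery |
| Stop | none stated | before any revision or re-tear |

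The listing has no stop rule, so the omitted events will be in the data. It is the counts that leave them out.

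**Inputs for scale (Section 2.1)**

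- Expected success rate: 0.85.
- Non-inferiority margin: 0.10, so the null rate is 0.85 − 0.10 = 0.75.
- One-sided alpha: 0.05.
- 103 evaluable subjects and 109 enrolled, allowing for 5% loss.

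**Reproducing the plan's own figure**

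The SAP says that "103 subjects will provide approximately 80% power for the one-sided exact binomial test at 0.05 significant level". Take the smallest r with P(X ≥ r | n = 103, p = 0.75) ≤ 0.05.

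- r = 84: P = 0.0742, too large.
- r = 85: P = 0.0456, so the test rejects at 85 or more successes.
- Power at p = 0.85: P(X ≥ 85) = 0.803.
- Exact one-sided 95% lower limit at 85/103: 0.752, which is above 0.75.
- Enrolment: 103 / 0.95 = 108.4, rounded up to 109.

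The stated 80% power and the 109 both reproduce.

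**Subjects to whom the cut applies** (expected failures = N × (1 − success rate))

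| Success rate | Of 103 | Of 109 |
|---|---|---|
| 0.95 (assumed) | 5.15 | 5.45 |
| 0.85 (planned) | 15.45 | 16.35 |
| 0.75 (null rate) | 25.75 | 27.25 |

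**Failures compatible with a positive study**

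103 − 85 = 18, and 18/103 = 17.5%. Passing the primary test therefore does not make the affected group negligible.

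**Failure events missing from the AE table**

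- None, if revisions and re-tears are not recorded as AEs.
- Up to about 15 of 103 at the planned rate, if all of them are.

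**Later AEs lost**

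This cannot be calculated, because the documents give neither AE rates nor failure times. The table above counts affected subjects, not lost events.

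**The case against.** The strongest reply is that nothing is hidden. Every AE appears in the listing, and this is a single-arm study of at most 109 subjects with no test or threshold on AEs. Revisions and re-tears are already the primary-endpoint failures, and Section 2.2 also plans a Kaplan-Meier summary of implant survival. That is all correct, and it limits the consequences. But a listing is not an incidence, and neither the primary endpoint nor the survival summary reports AEs that follow a failure.

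A second reply is attribution. After a revision, an AE may belong to the second operation rather than the study device, and symptoms after a re-tear may be consequences of a failure already counted. The first is a reasonable motive for stopping at a revision, but the SAP does not state it. It would not explain stopping at a re-tear that was never revised, where there is no second procedure to separate, nor leaving out the failure event. The second is also unstated, and a before/after split would show such events without deleting them.

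Third, the actual loss may be close to zero. Section 2.3 says: "The primary endpoint will be determined at the only clinical assessment, about one year from the index surgery". A re-tear first found at that visit leaves little later time in which AEs could be dropped. Whether failures are recorded as AEs at all depends on definitions these documents do not contain. Both points stand. They limit what can be said about size, but they do not reconcile the table with the objective.

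**Conclusion.** The concern holds. The planned AE tabulation does not measure the quantity in the safety objective, and where the two differ, the tabulated count is too low. This follows from the wording and rests on no numerical assumption.

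Its reach, at the planned success rate, is about 15 of 103 evaluable or 16 of 109 enrolled subjects. Its effect in numbers of AEs is unknown and could be small. That failure events themselves go missing is conditional on their being recorded as AEs.

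This should be fixed before analysis. It does not threaten the primary conclusion, since the primary test, the sample size and data collection are untouched.

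**What to change.** In Section 2.3, replace the sentence that sets the cut-off with text such as:

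> All AEs from index surgery through the one-year assessment will be summarised as number and percentage of subjects and number of events, overall and for device- and/or procedure-related AEs. Revisions and re-tears are counted in this table. Events will be split into those before, and those on or after, a revision or re-tear.

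The split keeps the sponsor's present cut available as a secondary table, so any attribution purpose is still served. If that purpose is the reason for the cut, the SAP should say so.

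The cost is one change of SAP wording and one extra table split, using AEs already due to be captured and listed. The reported AE rate will be the same or higher.

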2.2 General Statistical Methods

Continuous data, such as age, will be summarized by using means, medians, standard deviation, minimum, maximum, and 95% CI over the time periods of interest. Categorical data, such as gender or surgical approach, will be summarized by counts and percentages. Implant survival will be summarized using a Kaplan-Meier method and presented with rates (as percentages) and confidence intervals (CI). Statistical analyses will be performed using SAS 9.4. The binomial distribution tests will have 80% probability of computing a one-sided 95% lower confidence bound on survivorship of each device with a non-inferiority margin of 0.09. Patient confidentiality will be protected at all times, and patient identifiers will not be included in data summaries.

Handling of Missing and Incomplete Data: Data will be considered "censored" for the primary endpoint if the survivorship outcome cannot be determined or is unavailable for a subject. Every effort will be made to collect the data necessary to evaluate the primary endpoint. Patients who have been lost to follow-up will not be included in the primary study analysis at the end of 1 year. However, the data already collected will be used in interim analysis and survivorship calculations.

Sensitivity analyses will be performed to assess the impact of missing data on the primary study analysis. These analyses may include a best-case and worst-case imputation as well as a tipping point analysis.

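### The planned adverse-event summary does not separate out device- or procedure-related events, although the safety endpoint is defined by them, and it names no denominator

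*Combined protocol and SAP*

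**What the plan says.** Synopsis, Study Objectives/Endpoints: "The safety will be assessed by monitoring the incidence and frequency of device- and/or procedure-related adverse events". Safety is one of the three things the study sets out to confirm, with performance and clinical benefit.

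SAP section 2.3 contains the whole of the AE analysis:

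- Timing of collection: "Adverse events will also be captured at the one year assessment".
- Which events enter the summary: "Only AEs that occur on or after the index surgery and before any potential revisions or re-tears will be summarized".
- Form of the summary: "Adverse events will be presented as the number of cases for each AE and the number of times the give AE occurred".
- Listing: "Finally, a complete listing of all AEs will be presented".

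Two other sentences bear on the denominator. Section 2.3 defines a Per Protocol set (successful implantation) and adds: "Analyses on the primary and secondary endpoints will use this population as well as any exploratory analyses". Section 2.2 has a general rule: "Categorical data, such as gender or surgical approach, will be summarized by counts and percentages".

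**The concern.** The endpoint is defined by cause; the summary is defined by time. A table of every AE term between surgery and revision or re-tear, whatever its cause, measures something other than what the synopsis promises. For terms that may or may not be related to the anchor or the operation, such as infection or pain, the planned table cannot tell the reader how many cases belong to the endpoint.

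The base is also open. AEs are captured at a single assessment about one year after surgery, and 5% loss to follow-up is expected. A count of cases does not show how many subjects were observed. The study has no control group, so its safety conclusion will rest on the related-event figures themselves.

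**Working it through.** **1. The plan's own figures.** No figure is given for safety. The only sample-size figures concern healing, and they reproduce. With a null rate of 0.85 − 0.10 = 0.75, a true rate of 0.85 and n = 103, the exact one-sided test needs at least 85 successes, with type I error 0.0456 and power 0.803. Then 103 / 0.95 = 108.4, rounded up to 109. None of this depends on how AEs are tabulated.

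**2. Endpoint and analysis side by side.**

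| Element | Synopsis | SAP 2.2 and 2.3 |
|---|---|---|
| Which events | Related to device and/or procedure | Any AE from index surgery until revision or re-tear |
| Measure | Incidence and frequency | Cases and occurrences, per AE term |
| Relatedness split | Implied by the definition | Not mentioned in the summary or for the listing |
| Base | Not stated | Not stated for AEs; general percentage rule in 2.2 without a base |
| Population | Not stated | Per Protocol set for primary, secondary and exploratory analyses; no safety set named |

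The measure row agrees in form: cases correspond to incidence and occurrences to frequency. The first and third rows do not agree, and that alone means no planned summary isolates the endpoint. The last two rows leave the denominator to be chosen at the time of analysis.

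**3. What the missing table would show.** The counts below are assumptions, because the documents give no AE rate. Each percentage is x / N; the limits are exact (Clopper-Pearson), two-sided 95%.

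| Subjects with a related AE (assumed) | N = 109: % (95% CI) | N = 103: % (upper limit) |
|---|---|---|
| 0 | 0 (0 to 3.3) | 0 (3.5) |
| 1 | 0.9 (0.02 to 5.0) | 1.0 (5.3) |
| 5 | 4.6 (1.5 to 10.4) | 4.9 (11.0) |
| 10 | 9.2 (4.5 to 16.2) | 9.7 (17.1) |

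Moving from 109 to 103 shifts the percentage by at most about half a point (9.7 − 9.2 = 0.5). The interval is much wider than that: for 5 cases in 109 it spans 10.4 − 1.5 = 8.9 points.

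**The case against.** The best defence has five parts.

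- **Form.** Cases and occurrences are incidence and frequency under other names. This stands. A reader might infer that the SAP does not attempt the safety endpoint at all. The text does not support that: the right kinds of count are planned, without the restriction to related events or a stated base.
- **Denominator.** Having an AE is categorical, so the rule in 2.2 could supply percentages, and the Per Protocol set could be read as the base. This partly stands, so it would be too strong to say that percentages are excluded. But the rule's examples are gender and surgical approach, the AE sentence itself prescribes only counts, and neither text says what the base is. The Per Protocol set also requires successful implantation. Using it by default could leave out a subject whose implantation failed, where a related event is plausible.
- **Visibility.** A reader might infer that related events would be swamped by unrelated ones. The documents do not support this. They give no AE rates, and the table is by term rather than a grand total, so an anchor-specific failure would normally have its own line. The difficulty is confined to terms of ambiguous cause.
- **Text outside the SAP.** The synopsis is carried over from the approved protocol, which may hold causality definitions or limit reporting to related events. If reporting were so limited, the planned table would contain only related events before revision or re-tear. The documents here do not settle this, and 2.3 speaks of all AEs in the listing. A listing, even one that showed relatedness, is not a summary.
- **Interval.** The synopsis promises no confidence interval for safety and no safety hypothesis is tested. This stands: the lack of an interval contradicts nothing.

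**Conclusion.** The point holds for relatedness, and in a weaker form for the denominator. Followed exactly, section 2.3 gives per-term counts of AEs regardless of cause, so the safety endpoint in the synopsis is not isolated in any planned summary, and the base for a percentage is left unstated. This is a mismatch between a stated objective and a stated rule, and it should be corrected before analysis.

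Its size is modest. The endpoint is descriptive, and the choice between 109 and 103 changes a percentage by half a point or less at the counts examined. If causality is recorded, the table could be produced from the same data. The conclusion rests on the wording of the synopsis and of sections 2.1 to 2.3, and on relatedness being judged for each event, which the endpoint requires. It does not rest on any assumed AE count. The end of AE summarisation at revision or re-tear is a separate matter.

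**What to change.** In section 2.3, add as the main safety table: the number and percentage of subjects with at least one device-related AE, at least one procedure-related AE, and at least one AE related to either, with the number of events, by AE term. State the denominator as all subjects treated with the study device, and show how many of them have AE information. An exact 95% confidence interval for each percentage is a useful low-cost addition. Keep the table of AEs regardless of cause and the full listing as supportive output.

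The cost is one extra table shell and a little programming, using the causality judgement that the endpoint already needs. It requires no additional subjects or visits and leaves the sample size of 103 evaluable and 109 enrolled, and the primary test, unchanged.
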